### **Study Enrollment and Randomization**

Participants who complete the informed consent process will be enrolled in the trial. We will enroll consecutively until we reach a sample size of 160 subjects. The research nurse will assign a unique study identification number to each participant, collect demographic and clinical data from the EMR, administer a baseline questionnaire, and draw blood and collect urine. Participants will be randomized to either FANMI or Standard Care in a 1:1 ratio using a computer generated

random assignment. Subsequent monthly HIV visits for participants randomized to FANMI will be in the community center, and participants in the standard arm will be seen in the GHESKIO Adolescent Clinic.

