### Study Measures and Schedule

Characteristics	Month of Study Visit				
	0		6	12	>12
Demographic information	X				
HIV knowledge and beliefs	X		X	X	
HIV-related stigma	X		X	X	
HIV disclosure	X		X	X	
Social and family support	X		X	X	
Depression	X		X	X	
Alcohol and drug use	X		X	X	
Food insecurity	X		X	X	
Height, Weight	X		X	X	
WHO Stage	X		X	X	
New HIV related diagnoses	X		X	X	
CD4 T cell count	X		X	X	
Outcomes					
Alive and in care at 12 months (primary outcome)					X
Number of care visits attended			X	X	X
Plasma HIV-1 RNA level	X		X	X	
Time to ART initiation			X	X	
ART adherence			X	X	
Tenofovir-DP level			X	X	
Sexual risk behavior	X		X	X	
Sexually transmitted infections	X		X	X	
Pregnancy	X		X	X	
Health care utilization			X	X	

Participants in both study arms will complete three study visits with a research nurse at the GHESKIO Research Unit at enrollment, 6, and 12 months. Each study visit will include a questionnaire, extraction of clinic attendance and medical information from the GHESKIO EMR, and laboratory assessments. An HIV-1 RNA level will be measured at enrollment for research purposes and at 6 and 12 months per routine medical care. ART adherence measured by pill recall and Tenofovir-DP level in dried blood spots will be measured at 6 and 12 months after ART initiation. In addition to the four study visits, a subset of 30 participants in the FANMI arm will be recruited for qualitative interviews at 6 months and 12 months with [name] to assess acceptability of FANMI. (See section D.2.i for details of these interviews). This will entail two additional study visits for this subset of 30 people. The research team will also contact all participants who are not retained in care at 12 months (estimated 12 in FANMI and 32 in the standard arm) and invite them to return for a single study visit and qualitative interview to explore reasons for non-retention.

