estimation and inference about the hazard ratio. For repeated measures (condom use at each visit), we will use statistical methods suited for longitudinal data analysis – (generalized) linear mixed effect models that account for correlations within subject. Within these models, intervention, time and intervention\*time interaction will be included as covariates. For count data aiming at estimating rate (number of STIs), we will consider Poisson test and regression. When data are severely nonlinear, variable transformation (e.g., log) or nonparametric tests may be adopted, with justifications documented.

**Aim 2c:** Acceptability: All qualitative interviews will be transcribed verbatim, translated in English, and then entered into qualitative software (e.g. Atlas-ti) for coding and analysis. A thematic coding scheme will be created following the main points of the interview guide.

**Aim 2d:** Healthcare utilization and costs: Utilization will be summarized for each arm as descriptive counts such as number of HIV care visits, laboratory tests, medications, and hospitalizations. Unit costs will be determined for each type of healthcare utilization by applying labor rates and materials costs available from GHESKIO and other expense costs available from previous studies. Differences in costs between arms will be compared using non-parametric methods if required (e.g. Wilcoxon tests for medians, non-parametric bootstrap for means) due to the skewness often found in cost data.

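### The repeated-measures model for condom use leaves the month-0 arm difference free and names no effect contrast; holding the arms equal at month 0 would gain precision from data already planned.

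*Combined protocol and SAP*

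**What the plan says.** Under Aim 2b the Data Analysis section states: "For repeated measures (condom use at each visit), we will use statistical methods suited for longitudinal data analysis". The model class is (generalized) "linear mixed effect models that account for correlations within subject". The fixed effects follow in the sentence that begins "Within these models, intervention, time and" and ends "interaction will be included as covariates". That gives an arm main effect, a time effect and an arm-by-time interaction. The section does not mention a baseline covariate or an equal-baseline constraint for this model. It does not say whether time is categorical or linear, or which coefficient or contrast will be reported as the FANMI effect.

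The Study Measures and Schedule section provides for "three study visits with a research nurse at the GHESKIO Research Unit at enrollment, 6, and 12 months", and its table marks the row "Sexual risk behavior" at all three. In Study Enrollment and Randomization, the research nurse is to "administer a baseline questionnaire, and draw blood and collect urine", and the next sentence says: "Participants will be randomized to either FANMI or Standard Care in a 1:1 ratio".

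Condom use is the only outcome named for this model. Time to first pregnancy goes to Kaplan-Meier and Cox methods, and STI counts to Poisson methods.

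**The concern.** Taken together, these sections make month 0 a measurement taken before randomization and, on the natural reading, one of the rows of the outcome. With month 0 as the reference visit, the arm main effect is the difference between arms before any intervention. Individual 1:1 randomization makes that difference zero in expectation. Estimating it freely carries chance baseline noise into the treatment contrast. The interaction then becomes a difference in change from baseline.

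Three things are at stake:

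- Precision is lost in an analysis of 160 girls for which the Sample Size and Power section gives no power.
- Because no contrast is named, the coefficient labelled intervention could be reported as the effect when it is a pre-treatment difference.
- If time were entered as a straight line, half of the month-12 effect would be forced to appear at month 6.

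**Working it through.** **The plan's own figures.** The plan gives no power or precision for this model. Its stated power for the primary Fisher test (93% for 60% versus 85%, 80 per arm) reproduces at 93.3%, but that figure does not bear on this point.

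**Inputs from the documents.** 80 girls per arm, 1:1 allocation, visits at months 0, 6 and 12, and a forecast of 12 FANMI and 32 standard-arm participants not retained at 12 months (Study Measures and Schedule).

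**Assumption.** The within-girl correlation ρ between visits is not given. I use 0.3, 0.5 and 0.7, equal between any two visits, with equal variances.

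**Complete data.** Variances of the month-12 treatment contrast, categorical time, in units of σ²/n with n girls per arm:

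- Interaction (difference in change): 4(1−ρ)
- Month-12 arm difference from the same model (main effect plus interaction): 2
- Arms held equal at month 0: 2(1−ρ²)

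The third divided by the first is (1+ρ)/2. The third divided by the second is 1−ρ².

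| ρ | Change | Month 12 | Constrained | Constrained / change | Constrained / month 12 |
|---|---|---|---|---|---|
| 0.3 | 2.80 | 2.00 | 1.82 | 0.65 | 0.91 |
| 0.5 | 2.00 | 2.00 | 1.50 | 0.75 | 0.75 |
| 0.7 | 1.20 | 2.00 | 1.02 | 0.85 | 0.51 |

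The difference in change therefore needs 1/0.65 = 1.54, 1/0.75 = 1.33 or 1/0.85 = 1.18 times as many girls for the same precision. Below ρ = 0.5 it is also less precise than the plain month-12 difference, since 4(1−ρ) is then above 2.

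**With the forecast losses.** Suppose the 12 and 32 girls contribute month 0 only, leaving 68 and 48 with all visits. Let A = 80/68 + 80/48 = 2.843 (it is 2 with complete data).

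- Constrained: (1−ρ²)A = 2.587, 2.132, 1.450
- Change: (1−ρ²)A + 2(1−ρ)² = 3.567, 2.632, 1.630
- Month 12: (1−ρ²)A + 2ρ² = 2.767, 2.632, 2.430

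Constrained over change is 0.725, 0.81 and 0.89, so change needs about 38%, 23% and 12% more girls. Constrained over month 12 is 0.935, 0.81 and 0.60. Non-retained girls are invited back for a study visit and some may have month-6 data, so this is an upper bound on the loss from this source.

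**Power, for scale.** With 80 per arm, complete data, two-sided 0.05 and an assumed effect of 0.45 SD, power for change, month 12 and constrained is:

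- ρ = 0.3: 67%, 81%, 85%
- ρ = 0.5: 81%, 81%, 91%
- ρ = 0.7: 96%, 81%, 98%

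**Linear time.** With linear time and a random intercept, the constrained-to-unconstrained variance ratio for the interaction is 0.60, 0.73 and 0.84, close to the categorical case.

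**Binary check.** The formulas are for a linear model. A simulation used a logistic model fitted by GEE as a stand-in for the mixed model, with 300 runs per setting. It assumed 40% at month 0 in both arms, 45% versus 65% at month 12, 80 per arm and complete data.

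| Binary correlation | SD of log odds ratio: change / month 12 / constrained | Power: change / month 12 / constrained |
|---|---|---|
| 0.18 | 0.424 / 0.317 / 0.312 | 52% / 74% / 79% |
| 0.33 | 0.394 / 0.319 / 0.305 | 56% / 69% / 73% |

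Simulation error on these powers is about 2 to 3 points. The direction agrees with the formulas. Higher correlations were not checked this way.

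**The case against.** A model with arm, time and their interaction is standard and valid. A separate simulation under other assumed rates put type I error at 5.3% for the interaction and 5.7% with the constraint, so no error-rate problem is being repaired.

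A reader might infer that the plan defines the FANMI effect as a difference in change. The text does not say so. It lists covariates and stops. If the sponsor reports the month-12 arm difference from the same fit, the saving is only ρ²: 9% of the variance at ρ = 0.3 with complete data. In the binary check at correlation 0.33, most of the gain over the interaction (56% to 69%) comes from choosing the month-12 contrast, and a smaller part (69% to 73%) from the constraint. This stands, and it is why both sets of figures are given. It does not remove the point: the constraint gains something under either contrast, the gain over the month-12 difference rises to 25% or more once ρ reaches 0.5, and the contrast still needs naming. If month 0 were left out of the outcome rows, the baseline would go unused and precision would still be lost.

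A reader might also extend the point to all of Aim 2b. The documents do not support that, because pregnancy and STI counts have other methods. The remarks about linear time and about misreading the intervention coefficient are conditional on choices the plan leaves open; they are not errors in its text.

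**Conclusion.** The point holds as a free improvement to one secondary analysis. On the natural reading, the model for repeated condom use spends information on a month-0 arm difference that randomization sets to zero in expectation, and the plan leaves the effect contrast and the coding of time unstated.

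The size depends on which contrast is meant and on a correlation that the documents do not give. Over ρ from 0.3 to 0.7, the constraint removes 35% down to 15% of the variance of the interaction with complete data, or about 27% down to 11% if the forecast non-retained girls give month 0 only. Against the month-12 difference it removes 9% up to 49% with complete data. These are linear-model figures and approximate for binary condom use.

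A reader might conclude that the planned estimate is biased or that the trial is underpowered as a result. Neither follows. This is lost efficiency only, and the primary Fisher test, the viral load comparison and the sample size of 160 are unaffected.

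**What to change.** In Data Analysis, Aim 2b, replace the covariate sentence with text such as:

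> Month 0 is an outcome row. Time is categorical (0, 6, 12). The month-0 mean is common to both arms (no intervention main effect at month 0). The effect is the FANMI versus standard contrast at month 12, with month 6 supportive.

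Do not use the month-0 value as a covariate as if it were the same thing. In a linear model with complete data the two come to much the same. In a logistic model the covariate changes the odds ratio being estimated, and it drops any girl without a month-0 value.

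The cost is a few sentences before analysis and no new data. One condition goes with it: if condom use is analysed only among girls sexually active at a visit, randomization does not by itself justify equal arms at month 0. Define the outcome for all girls, for example any condomless sex in the recall period, so that it does.

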### **Sample Size and Power**

We performed sample size (N)/power calculation using the Fisher exact test for the primary outcome in the two independent prospective study arms. With alpha of 5% and with N=80 per arm, we will have 93% power to detect a difference between 60% vs. 85% per our primary hypothesis. If there is within cohort effect in the FANMI arm, then we will still have **83%** power to detect a difference in our primary outcome. If we assume potential average within-cohort correlation of 5% and cohort sizes of 5-10, the resulting variance inflation factor is 1.3 so that with N=80 per arm (or total N of 160), we will have 83% power to detect a difference of 60% vs. 85%. Our sample size will also provide reasonable power for important secondary analyses. We will have >80% power to detect a difference between 30% and 60% suppressed viral load at 12 months between the two study arms.

### **Timeline**

In months 1-3, we will finalize study operating procedures, data collection tools, and staff training. We will enroll participants in months 4-22 and complete all follow up visits by month 36. In months 36-42 we will conduct individual interviews, and complete laboratory assays. In months 43-48, we will finalize the data set and conduct analysis. Of note, all follow up visits will be completed by 36 months, and we will be able to report preliminary findings and begin planning for large scale implementation studies within three years of initiating this project.
